5.11.2. Secondary Efficacy Analyses

5.11.2.1. Key Secondary Efficacy Analyses

For OS, the same analyses used for the analyses of the primary PFS endpoint (except sensitivity analyses based on PFS censoring rule) will be performed. One interim analysis and a final analysis for OS may be performed in this study. A hierarchical testing procedure will be employed to test OS. The OS will be tested only if PFS is significant. If PFS is not significant after the primary analysis for PFS is performed, OS will not be statistically evaluated. This comparison of OS using the same method as that for the primary analysis of PFS will be considered inferential only in case of significant results for PFS analysis (that is, a gate keeping approach was used so as not to inflate the overall type I error rate).

The OS interim analysis may be performed at the time of primary PFS analysis (approximately 270 PFS events) and the final OS analysis may be conducted later with the aim of providing as much information as possible on OS. This final analysis of OS will be performed when OS data are relatively mature (approximately 300 OS events and 35% censoring). The 1-sided type I error rate will be controlled at 2.5% by using a Haybittle Peto type spending function (p-value bound 0.0001 at the interim analysis) (Jennison and Turnbull 1999).

5.11.2.2. Analyses of Other Secondary Efficacy Endpoints

The ORR and DCR (investigator and independent assessment) of each treatment arm will be calculated as defined by RECIST v1.1. Tumor response (CR+PR) rate and disease control (CR+PR+SD) rate will be reported along with exact confidence intervals (CI: 95%) and compared using the Cochran-Mantel-Haenszel test adjusting for the stratification variables.

Duration of response (investigator and independent assessment) will be compared between both treatment arms using unstratified log-rank test and Kaplan-Meier estimates. The DoR analysis is for responders only.

Patient listings of tumor assessments (target and non-target lesion assessments and tumor response) and DOR will also be provided.

5.11.3. Exploratory Efficacy Analyses

Time to deterioration in ECOG PS and its variations will be analyzed using the Kaplan-Meier method and compared using an unstratified log-rank test. The association between PFS event and ECOG PS deterioration will be assessed through an analysis of change from baseline in ECOG PS by objective progression (yes versus no) by tumor measurement period.

Time to diagnosis of CNS metastases will be analyzed using the Kaplan-Meier method and compared using an unstratified log-rank test for Part B only. For Part C, time to diagnosis of CNS metastases will be analyzed using the Kaplan-Meier method.

A waterfall plot of the (best) percent change from baseline in target lesion measurement will be generated for each study arm in Part B and Part C period 1.

Regarding PFS2 in Part B and PFS in Part C Period 2, the median with 95% CI, and progression free survival rates at various time points will be estimated using Kaplan-Meier method (Kaplan and Meier 1958).

A 1-year PFS rate of Part C, i.e., a cumulative proportion of patients who survived during the first year (that is, 1 year from enrollment) in the study without disease progression, will be estimated using Kaplan-Meier method (Kaplan and Meier 1958) in addition to PFS curves, the median with 95% CI, and survival rates at various time points, for Part B and C, respectively.

For PFS2 and OS in Part C Period 2, the median with 95% CI will be estimated using Kaplan-Meier method (Kaplan and Meier 1958) for patients that receive osimertinib after disease progression.

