Statistical Analysis Plan for Clinical Study I4T-MC-JVCY

A Multicenter, Randomized, Double-Blind Study of Erlotinib in Combination with Ramucirumab or Placebo in Previously Untreated Patients with *EGFR* Mutation-Positive Metastatic Non-Small Cell Lung Cancer

NCT02411448

Approval Date: 13-Dec-2018

1. Statistical Analysis Plan for Clinical Study: I4T-MC-JVCY: A Multicenter, Randomized, Double-Blind Study of Erlotinib in Combination with Ramucirumab or Placebo in Previously Untreated Patients with *EGFR*Mutation-Positive Metastatic Non-Small Cell Lung Cancer

Confidential Information

The information contained in this Statistical Analysis Plan (SAP) is confidential and the information contained within it may not be reproduced or otherwise disseminated without the approval of Eli Lilly and Company or its subsidiaries. This document and its associated attachments or appendices are subject to United States Freedom of Information Act Exemption 4.

Ramucirumab (LY3009806) Non-Small Cell Lung Cancer

This is a multicenter, randomized, double-blind, Phase 3 study that will compare the efficacy and safety of treatment with erlotin b (150 mg daily) and ramucirumab (10 mg/kg every 2 weeks) versus erlotinib (150 mg daily) and placebo (10 mg/kg every 2 weeks) in previously untreated patients with *EGFR* mutation-positive metastatic NSCLC. Treatment will continue until disease progression, unacceptable toxicity, or another permitted reason for study discontinuation. This Phase 3 part (Part B) is preceded by a Phase 1b part (Part A) to assess the safety and tolerability for the combination of ramucirumab plus erlotin b. In addition, Part C, an open-label, 2-period, single-arm, exploratory cohort is added to the main protocol.

Eli Lilly and Company Indianapolis, Indiana USA 46285 Protocol I4T-MC-JVCY Phase 1b/3

Statistical Analysis Plan (SAP) Version 3 electronically signed and approved by Lilly on date provided below.

SAP Version 2 electronically signed and approved by Lilly: 31 May 2018 SAP Version 1 electronically signed and approved by Lilly: 17 April 2015

Approval Date: 13-Dec-2018 GMT

2. Table of Contents

Section	Page
1. Statistical Analysis Plan for Clinical Study: I4T-MC-JVCY: A Multicenter, Randomized, Double-Blind Study of Erlotinib in Combination with Ramucirumab or Placebo in Previously Untreated Patients with EGFR Mutation-Positive Metastatic Non-Small Cell Lung Cancer	1
2. Table of Contents	2
3. Revision History	5
4. Study Objectives	7

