4.3. Exploratory Objectives

The exploratory objectives of both Parts B and C are to:

- assess the association between biomarkers and clinical outcome.
- assess progression-free survival 2 (PFS2).
- assess time to deterioration (TtD) in Eastern Cooperative Oncology Group (ECOG) performance status (PS)

- assess time to diagnosis of CNS metastases.
- progression-free survival 2 (PFS2) and overall survival (OS) analyses for patients who receive osimertinib after disease progression vs. those who do not.

The additional exploratory objectives of Part C only are to:

- evaluate the efficacy (for example, 1-year PFS rate) and safety of ramucirumab when administered in combination with gefitinib in previously untreated patients with EGFR mutation-positive metastatic NSCLC, in the East-Asian region including Japan
- evaluate the efficacy and safety of ramucirumab when administered in combination with osimertinib in patients with T790M-positive metastatic NSCLC and who have progressed on ramucirumab plus gefitinib in this study, in the East-Asian region including Japan
- assess pharmacokinetics (PK) and immunogenicity of ramucirumab
- assess patient-reported outcomes (using Lung Cancer Symptom Scale and EuroQol 5 dimension, 5-level questionnaire)

5. A Priori Statistical Methods

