Statistical analysis of this study will be the responsibility of Lilly or its designee. The study PK scientist will be responsible for designing, conducting, and interpreting the PK analysis and delivering PK parameters. The interpretation of final study results will be the responsibility of the clinical research physician (CRP) and the study statistician. These individuals will also be responsible for the appropriate conduct of an internal review process for both the CSR and any study-related material to be authorized for publication by Lilly.

The following general terms will be used globally in the SAP:

- Unless otherwise specified, **summary statistics** stand for n, mean, standard deviation, median, Q3-Q1, minimum, and maximum for continuous variables; and frequency and percentage for categorical variables.
- Study period

- O Dose-limiting toxicity (DLT) assessment period for Part A: for individual patient assessment, period begins on the day of the first study drug dose and ends on the day when the patient:
 - o completed 2 cycles of treatment, or
 - o discontinued from study treatment or study participation before completing 2 cycles due to a DLT.

Note. Two cycles are considered completed on the 14th day from the second dose of ramucirumab.

- o **Study treatment period** begins at the first dose of study treatment and ends when the patient and the investigator agree that the patient will no longer continue any study treatment. The date of this agreement is to be reported on the electronic case report form (eCRF) as the Date of Discontinuation from all study treatment.
- o **30-day short-term follow-up period** begins the day after the patient and the investigator agree that the patient will no longer continue any study treatment and lasts approximately 30 days (± 3 days).
- O Long-term follow-up period begins the day after short-term follow-up is completed and continues every 6 weeks (± 7 days) until progressive disease (PD), thereafter every 3 months (± 7 days) until the patient's death, withdrawal of consent to participate or overall study completion, whichever occurs first.

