5.3.4. Exploratory Analyses Variables

• Time to deterioration (TtD) in Eastern Cooperative Oncology Group (ECOG) performance status (PS) is defined as the time from the date of randomization to the first date observing a change (that is, deterioration) in ECOG PS to ≥2. Variations of the definition are: 1) a change to ≥3, 2) a change of ≥2 levels from baseline, and 3) a change of ≥1 level from baseline. Censor at time of the last ECOG PS value if no event.

- **Progression-Free Survival 2 (PFS2) (Part B)** is defined as the time from randomization to second disease progression (defined as objective radiological or symptomatic progression after start of additional systemic anticancer treatment), or death from any cause, whichever occurs first.
- Time to diagnosis of CNS (brain or meninges or spinal cord) metastases is defined as the time from randomization to CNS metastases. Patients without CNS metastases at the time of data inclusion cut off will be censored at the date of last postbaseline adequate radiological tumor assessment or at randomization if no post-baseline assessment.
- Time to response is defined as time from randomization to response (CR or PR) for those patients that responded only.

The exploratory analyses variables defined below are only applicable for Part C.

- 1-year PFS rate is defined as the cumulative proportion of patients who survived during the first year (that is, 1 year from enrollment) in the study without disease progression. Patients who have neither progressed nor died will be censored at the day of their last radiographic tumor assessment.
- Progression-free survival in Part C, Period 2 is defined as the duration from the date of last tumor measurement before osimertinib treatment to occurrence of PD or death from any cause, whichever occurs first.
- **PFS2 (Part C)** is defined as the duration from enrollment (assignment to treatment) to the second occurrence of PD or death from any cause, whichever occurs first.
- Overall survival (OS) in Part C, Period 2 is defined as the duration from the date of last tumor measurement before osimertinib treatment to the date of death. For each patient who is not known to have died as of the data cut-off date for a particular analysis, OS will be censored for that analysis at the date of last contact prior to the data-inclusion cut-off date (contacts considered in the determination of last contact date include AE date, lesion assessment date, visit date, and last known alive date).

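### Time to CNS metastases censors deaths and is estimated only by Kaplan-Meier, so a CNS incidence read from the curve will be too high

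*SAP*

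**What the plan says.** Section 4.3 lists, among the exploratory objectives of Parts B and C, to "assess time to diagnosis of CNS metastases". Section 5.3.4 defines the variable: it "is defined as the time from randomization to CNS metastases". Death is not part of the event. On censoring the same section says: "Patients without CNS metastases at the time of data inclusion cut off will be censored at the date of last postbaseline adequate radiological tumor assessment". A patient with no such assessment is censored on the day of randomization. No separate rule covers patients who die, so a death without CNS metastases falls under this one.

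Section 5.11.3 gives the analysis. For Part B: "Time to diagnosis of CNS metastases will be analyzed using the Kaplan-Meier method and compared using an unstratified log-rank test for Part B only". Part C gets the estimate without the test: "For Part C, time to diagnosis of CNS metastases will be analyzed using the Kaplan-Meier method". Neither Section 5.11.3 nor the sensitivity analyses in Section 5.11.5 mention a cumulative incidence function or any competing-risk method for this endpoint.

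**The concern.** Kaplan-Meier treats a censored patient as someone who could still have the event later, at the same rate as those still under observation. That is reasonable for a patient who is alive at data cut-off. It is not reasonable for a patient who has died, because a CNS metastasis can no longer be diagnosed. With deaths censored, one minus Kaplan-Meier estimates the CNS risk in a hypothetical population in which nobody dies, and then only if death and CNS metastasis are independent. It does not estimate the share of trial patients who are diagnosed.

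Death will not be rare here. Section 5.11.2.1 plans the final OS analysis at about 300 deaths, and Section 5.1.2 plans about 450 patients, so about two thirds will have died by then. PFS, DOR and PFS2 do not have this problem, because each counts death as an event.

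At stake is the CNS incidence that a reader takes from the curve. In Part B the log-rank test gives a second result. In Part C, which has a single arm, the Kaplan-Meier curve is the only CNS analysis planned.

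**Working it through.** **The plan's own figures.** The SAP states no figure for CNS metastases. The design figures in Section 5.1.2 reproduce: with 270 events, HR 0.71 and one-sided alpha 0.02499, the Schoenfeld formula gives 80.3% power (stated: at least 80%), and 11/0.71 = 15.5 months is a gain of 4.5 months, as stated. From Sections 5.1.2 and 5.11.2.1, the expected share of deaths at the final OS analysis is 300/450 = 67%.

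**Inputs for the CNS check, all assumed.** CNS hazard *c* = 0.01 per month, constant. Median overall survival *M* = 24 to 48 months, exponential, so the death hazard is *d* = ln 2/*M*. Death and CNS metastasis are independent, and scanning continues up to death or data cut-off. Horizon *t* = 24 months.

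**Formulas.**
- One minus Kaplan-Meier: 1 − exp(−*ct*)
- Cumulative incidence: *c*/(*c* + *d*) × [1 − exp(−(*c* + *d*)*t*)]

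**Results.** One minus Kaplan-Meier = 1 − exp(−0.24) = 21.3% in every row.

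| Median OS (months) | *d* | *c* + *d* | Cumulative incidence at 24 months | Factor |
|---|---|---|---|---|
| 24 | 0.0289 | 0.0389 | 0.2572 × (1 − 0.3933) = 15.6% | 1.37 |
| 36 | 0.0193 | 0.0293 | 0.3418 × (1 − 0.4955) = 17.2% | 1.24 |
| 48 | 0.0144 | 0.0244 | 0.4092 × (1 − 0.5562) = 18.2% | 1.18 |

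The factor hardly depends on the CNS hazard. At 0.005 per month it is 1.38 and 1.18 for median OS of 24 and 48 months. At 0.015 per month it is 1.36 and 1.17.

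**Does the factor differ between arms?** Keep the CNS hazard at 0.01 in both arms and take a control median OS of 36 months. With an OS HR of 1 the factor is 1.24 in both arms. With an assumed OS HR of 0.8, the ramucirumab death hazard is 0.8 × 0.0193 = 0.0154, its cumulative incidence is 18.0% and its factor is 1.19. So the arms differ only if survival differs, and the SAP assumes no OS hazard ratio.

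**Does the log-rank test still work?** A simulation of 4,000 trials used 225 patients per arm, the same CNS hazard in both arms (20% of ln 2/11), competing hazards that differed between arms, and administrative censoring at 12 to 36 months. The test rejected in 4.4% of trials at a nominal 5%. The Monte Carlo standard error is √(0.05 × 0.95/4000) = 0.34 percentage points, so this is consistent with the nominal level. The test compares cause-specific CNS hazards and is not undermined by independent competing events.

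**The case against.** The case for leaving the plan alone has four parts. The endpoint is exploratory and outside the PFS and OS hierarchy. The log-rank test is valid for what it compares. Section 5.11.3 asks for the Kaplan-Meier method but names no CNS median or percentage, so the SAP does not itself commit to a wrong incidence figure. Section 5.2 allows alternative methods and additional exploratory analyses. All four are correct and keep the severity low. They do not remove the point: Kaplan-Meier is the only estimator prespecified, and a CNS curve will be read as incidence, above all in Part C.

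A reader might infer something stronger: that non-CNS progression also acts as a competing event because scanning stops there, and that the overstatement is therefore larger and clearly unequal between arms. Taking the SAP's 11-month median and HR of 0.71 as total first-event hazards, with a CNS hazard of 0.01, the same formula gives 12.4% on placebo and 14.7% on ramucirumab, or ratios of 1.72 and 1.45 to the 21.3%. The document does not support this reading, for three reasons.

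- The SAP nowhere says that imaging ends at progression. Section 5.2 says only that follow-up runs every 6 weeks "until progressive disease (PD), thereafter every 3 months". PFS2 in Section 5.3.4 can rest on radiological progression after later therapy, and Part C Period 2 has its own PFS after first progression. The imaging schedule belongs to the protocol.
- Non-CNS progression does not prevent a later CNS metastasis. If scanning did stop there, it would be possibly informative censoring, with bias in either direction.
- The 12.4% and 14.7% are probabilities of CNS metastasis as the first event. That is a different quantity from the one Section 5.3.4 defines, so the ratios do not measure overstatement of the planned endpoint.

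**Conclusion.** The point holds for death. Deaths without CNS metastases are censored, Kaplan-Meier is the only estimator in Parts B and C, and one minus Kaplan-Meier read as CNS incidence is then too high. The size is about 1.2 to 1.4 times at 24 months, or 3 to 6 percentage points in the example (21.3% against 18.2% to 15.6%). This rests on the assumed CNS hazard, the assumed OS medians, constant and independent hazards, and continued scanning. The direction does not depend on the exact values. A difference in the factor between arms is possible but conditional on a survival difference, and should not be presented as expected.

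The Part B log-rank test does not need to be replaced. The primary PFS and the OS conclusions are unaffected. Severity is low.

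**What to change.** In Section 5.11.3, for Parts B and C, estimate CNS metastases by the cumulative incidence function (Aalen-Johansen), with death without CNS metastases as a competing event at the date of death. Patients alive without CNS metastases remain censored at the last adequate assessment. Amend the censoring sentence in Section 5.3.4 to separate the two groups, and state how a death long after the last adequate scan is handled, since CNS status is unobserved in that gap. Keep the Part B log-rank test and label it a comparison of cause-specific hazards.

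If an analysis that treats non-CNS progression as competing is wanted, label it separately as CNS as the first site of progression and do not report it as the CNS incidence. With equal CNS hazards, such an analysis shows more CNS first events in the arm whose patients stay progression-free longer, which could be misread as worse CNS control.

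The cost is a few sentences of SAP text and one more standard analysis, with no new data. The reported CNS percentages will be lower.

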5.11.4. Subgroup Analyses

Subgroup analyses will be performed for PFS, the primary endpoint, and OS. Only unstratified analysis will be performed on each subgroup. Each analysis will use the similar methodology as for the primary analysis. A Forest plot of the estimated HRs with 95% CIs will be provided for subgroups with sufficient number of events (≥ 15).

- all baseline stratification factors
- age (<65 years vs. ≥ 65 years)

- age (<70 years vs. ≥ 70 years)
- age (<75 years vs. ≥ 75 years)
- smoking history (ever vs. never smoker)
- performance status (0 vs. 1)
- initial stage at diagnosis (Stage IV vs. other)
- liver metastases (yes vs no)

Tobacco product smoking history will be collected. The definition of 'ever smoker' includes those who smoked ≥100 cigarettes, cigars, or pipe-fulls in his/her lifetime and the definition of 'never smoker' is one who smoked <100 cigarettes, cigars, or pipe-fulls in his/her lifetime.

Tests within each subgroup and tests for subgroup-by-treatment interaction terms will use an unstratified test and unstratified Cox PH model.

Additional subgroup analyses may be performed as deemed appropriate. If any safety analyses described in Section 5.15 identify important imbalances between arms, subgroup analyses of these endpoints may be performed.

CCI

The goal of subgroup analyses is to assess internal consistency of study results, and whether there is significant treatment heterogeneity across any of the subgroups. Appropriate interpretation is important since, even if all patient subgroups benefit to exactly the same extent in truth, smaller or larger estimated effects, even negative effects, may be seen for some subgroups simply by chance alone. Without appropriate interpretation, this can lead to erroneous conclusion in one or more subgroups, in particular where differential treatment effects are not expected across any of the factors assessed. In order to assist with interpretation of the subgroup results, the methodology of Fleming (1995) may be followed to provide background information on the extent of variability that might be expected by chance alone.

5.11.5. Sensitivity Analyses

The following sensitivity analyses will be performed:

- An analysis of PFS based on Blinded Independent Radiological Review.
 Discordance statistics, such as those defined by the Pharmaceutical Research and Manufacturers of America methodology (Amit et al. 2011) will also be calculated. These analyses will be conducted on all reviewed patients for Part B only.
- Comparison between the eCRF and IWRS values of the stratification factors corresponding to Part B will be performed.

- An analysis of investigator PFS will be estimated using an multivariate Cox PH model to be constructed by selecting variables among all the variables listed in Section 5.6 using stepwise selection method (for age, only include 65 as cut-off). The stepwise selection will use p-value <0.05 as the criterion for adding a variable and p-value ≥0.10 for dropping a variable. The treatment factor will be kept out of the model throughout the covariate selection process and only added into the final model. Hazard ratio for treatment effect and corresponding 95% CI will be estimated from the final model. Note. A covariate may be removed from the analysis if the number of patients representing one level of that variable is insufficient or data collected on that variable are incomplete. If a selected prognostic factor happens to be also a stratification factor, that factor will be used in stratification, instead of as a covariate in the model.
- An analysis of the primary investigator-assessed PFS stratified using the eCRF values instead of IWRS values.
- An analysis of investigator-assessed PFS using an unstratified log-rank test and unstratified Cox model
- An analysis of investigator assessed PFS based on the PP population
- An analysis of investigator assessed PFS without censoring for new anticancer therapy
- An analysis of investigator assessed PFS without censoring for missing 2 or more tumor assessments prior to PD/death
- An analysis of investigator assessed PFS counting clinical progression and radiographic PD as progression
- An analysis of primary investigator assessed PFS without censoring for missing 2 or more tumor assessments prior to PD/death and without censoring for new anticancer therapy.
- An analysis of investigator assessed PFS treating lost to follow up as progression
- An analysis of primary OS based on the PP population
- An analysis of the primary OS analysis stratified by the eCRF values
- An analysis of primary OS using an unstratified log-rank test and an unstratified Cox model
- An analysis of final OS censoring at the start of new anticancer therapy
- Similarly to PFS, an analysis of OS using a multivariate Cox PH model to be constructed by selecting variables among all the variables listed in Section 5.6 using stepwise selection method (for age, only include 65 as cut-off).
- A sensitivity analysis of ORR/DCR/DOR based on independent assessment will be conducted.

Additional post-hoc sensitivity analyses of PFS or OS may be performed as deemed necessary.

